		Amendment to the window allowance of Salvia pH samples taken on Day -7 as well as Ophthalmic tests performed during continuous dosing of AZD3965 treatment.
8.0	07 February 2017	Update to Part 2 of the study; including patient population, eligibility criteria, objectives and endpoints, investigations, schedule of events and sampling.
9.0	24 August 2017	Update to eligibility criteria; additional lactate and bicarbonate screening sample required as well as clarification to the Part 2 sampling assays.
10.0	18 December 2017	Clarification to Day -7 dose as this refers to the total dose administered on that day. This can be either once daily dosing or twice daily dosing.

Issue Date	Reason for update
	Update to the Part 1 and Part 2 Sampling Summaries to bring in line with the current protocol template.
29 May 2018	 Update to eligibility criteria: Additional guidance added to exclusion criteria #1 related to wash out periods for previous therapies. Additional guidance added to exclusion criteria #19 to include patients with low risk prostate cancer who are on surveillance. Fasting glucose has been updated from <6.1 mmol/L in the inclusion criteria for Part 2 of the study to <7.8 mmol/L. Patients with Type 1 diabetes controlled on insulin (but not oral anti-diabetic medication) can now be included in the study. IHC will be performed retrospectively once the patient has enrolled on the study rather than at pre-screening to confirm the patients' MCT1 and MCT4 expression. Expression is no longer part of the eligibility criteria. Update to exclusion criteria #15 to add further clarification and to allow patients with a first degree heart block to be included in the study. Update to exclusion criteria #16 to allow patients who have had a prior allogeneic bone marrow transplant. Removal of Day -7 dosing during Part 2 of the study and rearrangement of some on-study assessments to accommodate this. Lactate and bicarbonate testing added to Cycle 1 Day 1. Ophthalmology assessments removed from Part 2 of the study apart from best corrected visual acuity and ERG tests.
22 August 2018	CTA amendment 13 (incorporating Protocol version 11.0) was rejected by the MHRA on 03 July 2018. CTA amendment 14 (incorporating Protocol version 12.0) addresses the GNA points raised by the MHRA for CTA amendment 13. Protocol version 12.0 incorporates changes from Protocol version 11.0 plus:
	29 May 2018

Version No.	Issue Date	Reason for update			
		 Update to exclusion criteria #3 from 'known' to 'symptomatic brain or leptomeningeal tests' now classed as a substantial amendment. Mandatory ECG to be performed 24 hours after first dose of AZD3965. 			
13.0	27 March 2019	 Wording in inclusion criterion number 1, pertaining to Part 2 of the study has been updated from 'relapsed or refractory to conventional treatment' to 'relapsed or refractory or both to conventional treatment.' Definitions of DLBCL (diffuse large B cell Lymphoma) or BL (Burkitt's Lymphoma) relapsed and refractory added to inclusion criterion number 1, pertaining to Part 2 of the study. Update to exclusion criterion number 9; Update to exclusion criterion number 14; patients with Diabetes Mellitus Type 1 and Type 2 can be included on the study if they are diet controlled or insulin controlled with a fasting glucose <7.8 mmol/l and normal HbA1c. Use of potential prohibited concomitant medications can now be discussed on a patient by patient basis with the CDD and Cl in Part 2 of the study. Additional guidance regarding the use of prohibited concomitant medications during a break in AZD3965 dosing. A patient can re-start AZD365 only when 5 half lives of the prohibited concomitant medication has been reached. Addition of wording regarding SAEs to be reported when a patient is in pre-screening (SAEs only to be reported if related to study assessments i.e. biopsy). In Sections 7 and 9 of the protocol, the schedule of events and sampling for Part 1 of the study has been removed. See Protocol version 12.0 for Part 1 details. 			
14.0	04 February 2020	 Inclusion of requirement for continued patient benefit and physician review from Cycle 13 onwards. Annex 13 label has been updated to include PI name and site address, therefore Section 6.1 updated to reflect this change. Evaluations from Cycle 13 onwards added to Section 8.5. Section 8.8.1 Schedule of events for Part 2, Cycle 13 onwards added. 			

Version No.	Issue Date	Reason for update
		 CSR data cut off added to Section 14 and 15.5. Updated throughout to remove limit of 12 cycles. Blood volumes updated throughout to reflect Cycle 13 onwards.
		 General typographical and formatting updates throughout.

TABLE OF CONTENTS

TITLE PAGE TABLE OF CONTENTS LIST OF ABBREVIATIONS AND DEFINITION OF TERMS PROTOCOL SIGNATURES

1	PROTOCOL SUMMARY	15

17.6	APPENDIX	5:	Severe	valvular	heart	disease	(as	defined	by	British	Society	of
	Echocardiog	raph	ıy)								'	100

LIS	LIST OF ABBREVIATIONS AND DEFINITION OF TERMS			
	Abbreviation	Definition		
Α	ABPI	Association of the British Pharmaceutical Industry		
	AE	adverse event		
	ALP	alkaline phosphatase		
	ALT	alanine aminotransferase		
	ANC	absolute neutrophil count		
	AST	aspartate aminotransferase		
	ATP	adenosine tri-phosphate		
	AUC	area under the curve		
	AZ	Astra Zeneca		
в	Bid	"bis in die"- twice a day		
	BL	Burkitt Lymphoma		
	BP	blood pressure		
С	0C	degrees Celsius		
	CDD	Centre for Drug Development		
	СІ	Chief Investigator (formerly Co-ordinating Investigator)		
	Cmax	maximum observed plasma concentration		
	CR	complete response		
	CRA	Clinical Research Associate		
	eCRF	electronic case report form		
	CR-UK	Cancer Research UK		
	CSM	Clinical Study Manager		
	ст	computerised tomography		
	СТА	clinical trial authorisation		
	стс	circulating tumour cell		
	CTCAE	Common Terminology Criteria for Adverse Events		
	ctDNA	circulating tumour deoxyribonucleic acid (DNA)		
	CXR	chest x-ray		
D	Day	calendar day		
	DBP	diastolic blood pressure		
	DLBCL	diffuse large B cell lymphoma		
	DLT	dose limiting toxicity		
Е	ECG	electrocardiogram		
	ECHO	echocardiogram		
	EDC	electronic data capture		
	EDTA	ethylene diamine tetra-acetic acid		
	EF	ejection fraction		
	EP	early progression		
	ERG	electroretinogram		
F	FDG	fluorodeoxyglucose		
	ffERG	full field electroretinogram		
G	GCP	Good Clinical Practice		
	g/dL	gram(s) per decilitre		
_	GMP	Good Manufacturing Practice		
Н	Hb	haemoglobin		
	HBF	hepatic blood flow		
	hERG	Human Ether-a-go-go Related Gene		
	HCG	human chorionic gonadotropin		
	HI∨	human immunodeficiency virus		
	HNSTD	highest non seriously toxic dose		
	HR	heart rate		
	HRA	Health Research Authority		

LIST OF ABBREVIATIONS AND DEFINITION OF TERMS

	Abbreviation	Definition
	IB	Investigator's Brochure
	ICH GCP	International Conference on Harmonisation of Good Clinical Practice
	IHC	Immunohistochemistry
	IMP	investigational medicinal product
	ITF	Investigator Trial File
	IUD	Intra-uterine device
	IWG	international working group
Κ	kg	kilograms
	LDH	lactate dehydrogenase
	L-HPC	low-substituted hydroxylpropyl-cellulose
	LVEF	left ventricular ejection fraction
M	MAD	maximum administered dose
	МСТ	monocarboxylate transporter
	MDR	multi-drug resistance
	min	minutes
	mg/m ²	milligram per square metre
	mg	milligrams
	mL	milliliters

1 PROTOCOL SUMMARY

1.1 Full title

A Cancer Research UK Phase I trial of AZD3965, a monocarboxylate transporter 1 inhibitor (MCT1) in patients with advanced cancer.

1.1.1 Short title

A Phase I trial of AZD3965 in patients with advanced cancer.

1.2 Clinical trial objectives and endpoints

1.2.1 Primary objectives and endpoints

Primary Objectives	Endpoints
1. To propose a recommended Phase II dose (RP2D) of AZD3965 and/or the maximum tolerated dose (MTD) in patients with advanced cancer, given via oral administration	1. Determining a dose at which no more than one patient out of up to six patients at the same dose level experiences a highly probable or probably drug-related dose limiting toxicity (DLT) and/or a biological effective dose based on pharmacokinetic (PK) and pharmacodynamic (PD) endpoints.
2. Establishing the safety profile of AZD3965	2. Determining causality of each adverse event to AZD3965 and grading severity according to the National Cancer Institute Common Terminology Criteria for Adverse Events (NCI CTCAE) version 4.02.

1.2.2 Secondary objectives and endpoints

Secondary Objectives	Endpoints
1. To investigate the pharmacokinetic (PK) behaviour of AZD3965 in patients with advanced cancer	1. Determining the plasma levels of AZD3965 after single and multiple doses of AZD3965.
2. Part 2: To assess the potential anti-tumour activity of AZD3965 in patients with relapsed or refractory diffuse large B cell Lymphoma (DLBCL) and/or Burkitt Lymphoma (BL)	2. Objective response: stable disease (SD), partial response (PR), or complete response (CR) according to Response Criteria Evaluation (RECIST, version 1.1) or International Working Group criteria for Lymphoma (see appendix 2A and 2B).

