3.1.2 Secondary objectives and endpoints

Secondary Objectives	Endpoints
	1. Determining the plasma levels of AZD3965 after single and multiple doses of AZD3965,

•	2. Objective response: SD, PR, or CR according to RECIST, (version 1.1) or International Working Group criteria for Lymphoma (see Appendix 2A and 2B),
---	--

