3.2 Patient evaluability

Part 1:

All patients that met the eligibility criteria and take at least one dose of AZD3965 were evaluable for safety decisions.

[figure not shown]
Patients who received less than 75% of their first continuous treatment cycle (for reasons other than toxicity) would not be evaluable for dose escalation decisions. Patients who completed 75% of their first continuous treatment cycle but did not complete the end of Cycle 1 ERG and ophthalmology assessments could also not be evaluable for dose escalation decisions. This was discussed on a per patient basis between the Investigator, Chief Investigator (CI) and CDD.

Part 2:

All patients that meet the eligibility criteria and take at least one dose of AZD3965 will be evaluable for safety decisions.

All patients who meet the eligibility criteria and take at least 75% of their first continuous treatment cycle (28 days) of AZD3965 and have a baseline assessment of disease will be evaluable for response.

To be assigned a status of complete response (CR) or partial response (PR), changes in tumour measurements must be confirmed by repeat measurements performed no less than four weeks after the response criteria are met. To be assigned a status of stable disease (SD), follow-up measurements must have met the SD criteria at least once and at least six weeks after the initial dose of the IMP AZD3965 is given.

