4 PATIENT SELECTION

4.1 Eligibility criteria

The patient must fulfil the eligibility criteria (listed in Sections 4.1.1 and 4.1.2).

4.1.1 Inclusion criteria:

- 1. Part 1:
 - Histologically or cytologically proven advanced solid tumour or Lymphoma, refractory to conventional treatment or for which no conventional therapy exists (if the diagnosis is confirmed by cytology and no follow-up historical tumour sample has been obtained, the patient will not be eligible).
 - Available archived tumour samples.

Part 2:

- Histologically proven DLBCL or BL, which is relapsed or refractory or both to conventional treatment or for which no conventional therapy exists or has been refused by the patient. (Refractory disease is defined as either progressive disease as the best response to the last line of systemic therapy or stable disease as the best response after at least two cycles of the last line of therapy with stable disease duration lasting no longer than six months from the last dose of the last line of systemic therapy. Relapsed disease is defined as disease that responded partially or completely to the last line of therapy and has since progressed).
- Confirmed available tumour samples which can be obtained and used for the study to confirm MCT1 and MCT 4 expression (it is acceptable for the result to be reported after the patient has started study treatment) as demonstrated by IHC.
- Measurable disease according to RECIST criteria version 1.1 or International Working Group criteria for Lymphoma
- 2. Life expectancy of at least 12 weeks
- 3. World Health Organisation (WHO) performance status of 0 or 1 (Appendix 1)
- 4. Haematological and biochemical indices within the ranges shown below.

Laboratory Test	Value required (For both Parts 1 and 2 except where specified)
Haemoglobin (Hb)	\geq 9.0 g/dL (90 g/L) or \geq 10.0 g/dL (100 g/L) if transfusion within last 4 weeks
Absolute neutrophil count (ANC)	Part 1: ≥ 1.5 x 10 ⁹ /L Part 2: ≥ 1.0 x 10 ⁹ /L
Platelet count	Part 1: ≥ 100 x 10 ⁹ /L Part 2: ≥ 50 x 10 ⁹ /L
Serum bilirubin	\leq 1.5 x upper limit of normal (ULN)
Alanine amino-transferase (ALT), aspartate amino-transferase (AST) and alkaline phosphatase (ALP)	\leq 2.5 x ULN or \leq 5 x ULN in presence of liver metastases (ALP \leq 5 x ULN in presence of bone metastases)
GFR	

Either:	
Calculated creatinine clearance (using the Wright or Cockcroft-Gault formula)	≥ 50 mL/min
Or :	
Isotope clearance measurement	
(uncorrected)	

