5.7 Duration of treatment

Treatment should continue for six cycles unless (a) the patient asks to be withdrawn, (b) there is evidence of disease progression (c) the patient is experiencing unacceptable toxicity or (d) the Investigator feels the patient should be withdrawn from any other reason including those listed in Section 12.

If a patient is benefiting from treatment with AZD3965 (i.e. has stable or responding disease as measured by RECIST version 1.1 or International Working Group criteria for Lymphoma) and the patient is not experiencing any Grade 2 or greater drug-related AEs then the CI and / or Principal Investigator (PI) can ask the CDD if the patient can continue with treatment. The CDD will request a full toxicity profile of that patient when considering the request. Should the decision be to allow further treatment, 6 further cycles may be given. After completion of 12 cycles, a further review will be conducted by the Sponsor, CI and treating clinician(s). A patient may continue on study as long as they are benefiting from treatment with AZD3965 and IMP stock is available. If the CDD decides not to allow the patient to

continue treatment, based on the information provided or on other information received, then the CDD's decision is final.

For the purposes of this trial a patient who completes six or more treatment cycles is considered to have completed the trial.

For patients who continue on study for extended treatment, i.e. for longer than 6 or 12 cycles, these patients must continue to show that benefit is being derived from receiving AZD3965. After each disease assessment the PI will relay findings to CDD for this determination to be met.

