- Pattern and full-field ERG (light and dark adapted) (or equivalent ERG assessment as previously agreed with the CDD) to be performed at the end of Cycle 1 ±3 days and then repeated every 28±3 days if the patient reports symptoms of eye toxicity/changes in their vision.
 ERGs can be stopped after the end of Cycle 1 if no symptoms are reported and the Ophthalmologist agrees no further ERG testing is required;
- Assessment of disease (radiological, clinical if applicable, and tumour markers): This must be repeated at the end of every 2 cycles (±3 days) unless assessment has been performed within the previous 4 weeks (28 days).

PLEASE NOTE: If patient presents with disease progression, assessment of tumour disease should be performed at the last study visit unless assessment has been performed within the previous four weeks (28 days). If assessment is to be conducted on Cycle 1 Day 29 (or Day 1 Cycle 2), assessment must be performed prior to the fresh (new) on study paired tumour biopsy.

Blood PK assays: see Section 9.

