11.3 Tumour response

All patients who meet the eligibility criteria and receive at least 75 % of their first cycle of trial medication and have a baseline assessment of disease will be evaluable for response. To be assigned a status of CR or PR, changes in tumour measurements must be confirmed by repeat measurements performed no less than four weeks after the response criteria are met. To be assigned a status of stable disease (SD), follow-up measurements must have met the SD criteria at least once and at least six weeks after the initial dose of the investigational medicinal product (IMP) AZD3965 is given.

Should rapid tumour progression occur before the completion of 4 weeks, the patient will be classified as having early progression (EP).

Tumour response should be classified as "not evaluable" (NE), only when it is not possible to classify it under another response category, for example, when baseline and/or follow-up assessment is not performed or not performed appropriately.

Expert reviewers appointed by CDD may undertake an independent review of all the Investigator's assessed objective responses (CR and PR). The expert reviewers will include at least one specialist who is not an Investigator in the trial. In case of disagreement between the Investigator's and the expert

reviewers' assessment, discussion will take place between the two parties in order to reach a consensus. However, if it is not forthcoming, the assessment of the expert reviewers will be retained in the clinical study report. The eCRF will reflect the Investigator's opinion.

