2.3.1. Evaluation of target lesions

Complete Response (CR): Disappearance of all target lesions. Any pathological lymph nodes (whether target or non-target) must have reduction in short axis to <10 mm.

Partial Response (PR): At least a 30% decrease in the sum of diameters of target lesions, taking as reference the baseline sum diameters.

Progressive Disease (PD): At least a 20% increase in the sum of diameters of target lesions, taking as reference the smallest sum on study (this includes the baseline sum if that is the smallest on study). In addition to the relative increase of 20%, the sum must also demonstrate an absolute increase of at least 5 mm. (Note: the appearance of one or more new lesions is also considered progression).

Stable Disease (SD): Neither sufficient shrinkage to qualify for PR nor sufficient increase to qualify for PD, taking as reference the smallest sum diameters while on study.

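### The Part 2 secondary endpoint counts stable disease as objective response, against Section 11.3, and leaves RECIST or lymphoma criteria open for an all-lymphoma cohort

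*Protocol*

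**What the plan says.** Section 1.2.2 pairs an objective labelled Part 2, in relapsed or refractory DLBCL and/or Burkitt lymphoma, with the endpoint "Objective response: stable disease (SD), partial response (PR), or complete response (CR) according to Response Criteria Evaluation (RECIST, version 1.1) or International Working Group" criteria. Section 3.1.2 restates it: "Objective response: SD, PR, or CR according to RECIST, (version 1.1) or International Working Group criteria for Lymphoma".

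Other parts of the protocol use the terms differently:

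- Section 11.3 provides for optional expert review of the Investigator's "assessed objective responses (CR and PR").
- Section 5.7 speaks of a patient who "has stable or responding disease as measured by RECIST version 1.1 or International Working Group criteria for Lymphoma", so stable and responding are separate states.
- Appendix 2B, the lymphoma criteria, heads its SD category as no response.
- Sections 3.2 and 11.3 require CR and PR to be confirmed by a repeat at least four weeks later. For SD, "follow-up measurements must have met the SD criteria at least once and at least six weeks after the initial dose".

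Section 14.5 places objective responses, best response and time to progression in the data listings. It does not say which categories make an objective response.

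On the criteria, the Part 2 inclusion bullet in Section 4.1.1 also reads "Measurable disease according to RECIST criteria version 1.1 or International Working Group criteria for Lymphoma". Section 11.1 allows either set. Appendix 2A is headed for solid tumours and Appendix 2B for lymphoma.

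**The concern.** An endpoint row should fix which patients count. Here the row and Section 11.3 give different answers for every patient whose best result is SD, and the analysis section does not settle it. If the listing follows Section 1.2.2, patients whose disease merely did not progress appear beside confirmed responders. They do so on lighter evidence, and they fall outside the expert review in Section 11.3, which covers CR and PR only.

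The open choice of criteria is a second and smaller problem. RECIST sums diameters, using the short axis for nodes. The CT-based lymphoma rules use products of perpendicular diameters and judge progression lesion by lesion. A row written only for lymphoma patients should not leave that choice open, because it can change both the response class and the listed date of progression.

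**Working it through.** The protocol gives no response rate, test or sample size for this endpoint, so there is no figure to reproduce. The check is textual, followed by arithmetic on the two sets of thresholds.

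**1. Which categories count as objective response**

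| Place | Counts as response |
|---|---|
| 1.2.2 and 3.1.2 | SD, PR, CR |
| 11.3 | PR, CR |
| 5.7 | responding disease, named apart from stable |
| 4.1.1, definition of relapse | prior partial or complete response |
| Appendix 2B | SD falls under no response |
| 14.5 | not defined |

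The endpoint row stands alone.

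**2. One patient traced through the text**

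Take an evaluable patient with a single SD assessment at least six weeks after first dose, then progression. Under 1.2.2 this is an objective response, and under 11.3 it is not. The best-response listing shows SD either way. No repeat is required, whereas a CR or PR needs one at least four weeks later.

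**3. Whether the choice of criteria can change the class**

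Thresholds from the appendices:

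- RECIST progression is "At least a 20% increase in the sum of diameters of target lesions" from the smallest sum, plus at least 5 mm. RECIST PR is a 30% decrease.
- CT-based lymphoma progression in a lesion over 2 cm needs a longest diameter above 1.5 cm, a product at least 50% above nadir, and a 1.0 cm increase in either diameter. PR is a decrease of at least 50% in the sum of products.

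The sizes below are invented for illustration. Baseline is the nadir, and there are no new lesions and no change elsewhere.

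*Example A: two extranodal lesions of 30 × 30 mm, each growing 21% per axis.*
- New diameter: 30 × 1.21 = 36.3 mm.
- RECIST: the sum goes from 60 to 72.6 mm, which is +21% and +12.6 mm, so progression.
- Lymphoma CT: 36.3² / 30² = 1.464, so the product rises 46% (below 50%). The diameter rises 6.3 mm (below 10 mm). The class is SD.

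*Example B: five extranodal lesions of 30 × 30 mm in at least three organs, one growing to 41 × 41 mm.*
- RECIST: (4 × 30 + 41) / 150 = 161 / 150 = 1.073, so +7.3% and SD.
- Lymphoma CT: 41² / 30² = 1.868, so the product rises 87% and the diameter 11 mm. The class is progression.

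*Example C: one node going from 40 × 20 mm to 24 × 16 mm.*
- RECIST: the short axis goes from 20 to 16 mm, which is −20%, so SD.
- Lymphoma CT: (24 × 16) / (40 × 20) = 384 / 800 = 0.48, so −52% and PR.

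Examples A and B change whether the patient counts even under the endpoint as written. Example C matters only once response means CR or PR. With uniform shrinkage the two PR cut-offs nearly coincide: a 30% fall in diameter is 1 − 0.7² = 51% in product.

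**The case against.** The best defence is that little depends on this. The endpoint is secondary, Section 14.1 makes the presentation descriptive, and Section 14.5 plans patient listings. Section 11.3.1 has the category recorded at each assessment and Section 14.5 lists best response, so anyone can count CR plus PR. That stands, and it limits the weight. It does not make the definition right.

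On the criteria, the appendix headings already steer lymphoma patients to Appendix 2B, and nothing shows that any Part 2 patient would be classed by RECIST. The either/or wording is legitimate in Sections 5.7 and 11.1, which also serve Part 1, where solid tumours or lymphoma were admitted. The objective cells of Section 3.1.2 are blank in the text at hand, so its tie to Part 2 comes from Section 1.2.2. All of this is fair. What remains is that the Part 2 row and the Part 2 inclusion bullet expressly offer RECIST, and no operative sentence assigns Appendix 2B.

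A reader might infer more than the documents support:

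- **That the first scan always satisfies the six-week SD rule, while a CR or PR must wait for a much later scan.** Section 8.4 does say of the disease assessment, "This must be repeated at the end of every 2 cycles (±3 days"). But it also contemplates an assessment at Cycle 1 Day 29 and waives a scan when one was done in the previous 28 days. Section 11.2.2 allows earlier scans when clinically indicated. No fixed earliest day follows.
- **That a reported response rate would be inflated by a given amount.** No rate is planned, and any counts would be invented.
- **That the imaging basis is left open.** Section 8.1.3 assigns baseline FDG-PET/CT to patients with PET-avid disease, and Section 11.2 requires the same methods and identical techniques throughout. That largely settles it.
- **That a rule for unconfirmed responses is missing.** Such detail commonly belongs in the statistical analysis plan, which is not at hand.

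**Conclusion.** The endpoint definition is wrong as written. Sections 1.2.2 and 3.1.2 count SD as objective response, Section 11.3 does not, and Section 14.5 does not resolve it. The effect is that every patient with a qualifying SD, and no confirmed CR or PR, could be listed as an objective responder. How many that would be cannot be known from the protocol. The unassigned criteria set is a real but lesser defect. The CT examples show that it can move a patient between classes in either direction, but they rest on assumed lesion sizes and say nothing about how often this happens. The point deserves correction because the error is clear and the remedy is cheap. It does not threaten the trial's primary objectives.

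**What to change.** - In Sections 1.2.2 and 3.1.2, define objective response as confirmed CR or PR, in line with Section 11.3. List CR+PR+SD separately as disease control, under the existing six-week SD rule.
- In Sections 1.2.2, 3.1.2 and 11.1, state that the Part 2 response and time-to-progression analysis is classified by Appendix 2B. Part 1 wording need not change.
- The sponsor should reconcile the either/or wording in Section 4.1.1 (eligibility) and Section 5.7 (continuation of treatment) with this. No choice is proposed for those rules.

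The cost is protocol wording and no new scans. Any Part 2 patient already classed by RECIST must be reclassified. Sections 11.2.1 and 11.2.2 require lesion measurements on the scan reports, so part of this can be done from recorded measurements where both diameters are given. The rest can use the scans retained under Section 15.6. The sponsor also accepts a less favourable objective-response listing, since SD patients leave it.
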